6.2. General Considerations

Statistical analysis of this study will be the responsibility of Eli Lilly and Company (Lilly) or its designee. Any change to the statistical methods described in the protocol will require a protocol amendment only if it changes a principal feature of the protocol. Any other change to the statistical analyses and the justification for the change will be documented in this SAP.

Unless otherwise specified, safety analyses will be conducted on safety population ([Table GPHG.2](#)) and pharmacodynamic (PD) analyses will be conducted on PD analysis set ([Table GPHG.2](#)).

Unless otherwise noted, all tests of treatment effects will be conducted at a 2-sided alpha level of 0.05, and the CI will be calculated at 95%, 2-sided.

If deemed necessary, additional analyses (e.g. linear mixed-effect models) of the endpoints on log transformed data will be conducted.

6.3. Patient Characteristics

The following patient demographic and clinical characteristics at study baseline (measurement collected at screening Visit 1 or during Period 1 Visit 3 Day 1 before first dose; details see below) will be summarized for the safety population and for PD analysis set by treatment sequence (i.e. tirzepatide/placebo and placebo/tirzepatide) and overall.

- age (years)
- age (<65, \geq 65 years)
- sex (male, female)

- race
- ethnicity (Hispanic or Latino, Not Hispanic or Latino)
- height (cm)
- duration of diabetes (years)

Note: for above parameters, the measurement collected at screening Visit 1 will be used.

- body weight (kg)
- body mass index (BMI) (kg/m²)
- BMI groups (<30, ≥30 to <35, and ≥35 kg/m²) and (<27, ≥27 kg/m²)
- hemoglobin A1c (% and mmol/mol)
- fasting glucagon
- fasting insulin
- fasting C-peptide
- fasting glucose
- systolic blood pressure
- diastolic blood pressure
- pulse rate

Note: for above parameters, the measurement collected during Period 1 Visit 3 Day 1 before first dose will be used.

In addition, the following patient clinical characteristics at baseline for each period will be summarized for the safety population and for the PD analysis set by treatment for each period, and by treatment (i.e. placebo: overall, period 1, period 2; tirzepatide: overall, period 1, period 2).

- body weight (kg)
- body mass index (BMI) (kg/m²)
- hemoglobin A1c (% and mmol/mol)
- fasting glucagon
- fasting insulin
- fasting C-peptide
- fasting glucose
- systolic blood pressure
- diastolic blood pressure

- pulse rate

Note: for above parameters, the measurements collected during Period 1 Visit 3 Day 1 before first dose and Period 2 Visit 10 Day 1 before first dose will be used.

6.4. Patient Disposition

A listing of patient disposition for the randomized population will be provided. Patient disposition will be summarized by treatment sequence and period.

A listing of patients who discontinue from the study for any reason for the randomized population will be provided, and the extent of their participation in the study will be reported. The reason for their discontinuation from study will be reported. The listing will also include age, sex, race, treatment, and study period.

6.5. Concomitant Therapy

Concomitant medication will be listed and summarized by World Health Organization Drug Dictionary Medication Class and Preferred Term for the safety population.

A listing of rescue medication for hyperglycemia will be provided.

6.6. Treatment Exposure and Compliance

6.6.1. Treatment Exposure

The duration of exposure to study medication (tirzepatide or placebo) in each treatment period is defined as:

Date of last dose of study medication - date of first dose of study medication + 7 days

The duration of exposure to study medication for each treatment period will be listed and summarized by treatment for each treatment period and by treatment only using the safety population

6.6.2. Treatment Compliance

Treatment compliance will be assessed using the safety population. Treatment compliance for each patient will be listed, including the percent compliance for 12-week treatment period taking into account early termination. Percent compliance and treatment compliance will be summarized by treatment for each period and by treatment only.

The percent compliance will be calculated as:

*(Number of injections administered [regardless of actual dose in mg administered]
÷ total number of injections expected to be administered) × 100*

Patients will be considered treatment compliant if taking $\geq 75\%$ of their scheduled doses for 12-week treatment period taking into account early termination (specifically excluding the period after early termination).

When assessing treatment compliance, the missed doses and interrupted doses will be taken into consideration as described in protocol (Section 7.2.1 Selection and Timing of Doses and Section 8.1.2 Temporary Interruption of Study Drug).

6.7. Important Protocol Deviations

Important protocol deviations (IPDs) are defined as deviations from the study protocol that may significantly compromise the data integrity and/or patients' safety. The details of identification of IPDs is provided in a separate document (i.e., the trial issue management plan). A listing/table of IPDs will be provided by the study manager after database lock.

6.8. Pharmacokinetic Analyses

6.8.1. Pharmacokinetic Parameter Estimation

Pharmacokinetic (PK) samples will be collected across the study duration. Tirzepatide concentrations will be determined to support an understanding of tirzepatide exposure over the treatment duration to compare with expected tirzepatide PK.

6.8.2. Pharmacokinetic Statistical Inference

No non-compartmental analysis dependent PK parameters will be derived, thus no statistical analyses of PK parameters are planned.

6.9. Pharmacodynamic Analyses

6.9.1. Pharmacodynamic Parameter Estimation

Hypoglycemic Clamp Procedure Measurements

The clamp procedure will be initiated on Day 79 (clamp run-in period) and the hypoglycemic induction will be performed on Day 80 at the end of both treatment periods. The patient will be asked to attend the clinical research unit at approximately 18:00 hours in the evening of Day 79 and will be served a standardized dinner at approximately 19:00 hours and thereafter will be fasted until the end of the clamp procedure on Day 80.

Pharmacodynamic assessments will include counter-regulatory hormone responses (glucagon, growth hormone, cortisol, adrenaline, and noradrenaline), and responses of insulin and C-peptide before and/or during the clamp, as well as clinical hypoglycemia (hypoglycemic symptom score and hypoglycemia awareness), time to hypoglycemia recovery, vital signs during induced hypoglycemia, and other hypoglycemic clamp and recovery parameters.

During the hypoglycemic clamp, for safety considerations, if the target PG concentrations are not achieved within 30 minutes of completion of the previous step, a higher PG concentration will be accepted as the PG concentration at which assessments are conducted. In case PG nadir 45 mg/dL (2.5 mmol/L) target cannot be reached or symptoms of hypoglycemia are unacceptable, nadir at a higher PG concentration will be accepted (decision will be made by site personnel conducting the test) and data will be included in the analyses.

Hypoglycemic clamp

Clamp interventions are based on the mean PG reading (recorded in eCRF) as one blood sample will be measured twice. The actual times (24 hour clock) of each stage of clamp procedure for each patient are provided through eCRF. These actual times, corresponding to key clamp timepoints (see [Table GPHG.3](#) for details) will be identified by programming.

Table GPHG.3. Key Timepoints of Hypoglycemic Clamp Procedure On Day 80

Clamp PG Level	Planned Key Timepoints	eCRF Clamp Procedure Stage Comment
100 mg/dL (5.5 mmol/L)	-30 minutes	Start plateau 5.5 mmol/L
End of 100 mg/dL (5.5 mmol/L)	0 minutes	Stop plateau 5.5 mmol/L
Reaching 63 mg/dL (3.5 mmol/L)	I minutes	Start plateau 3.5 mmol/L
End of 63 mg/dL (3.5 mmol/L)	I +30 minutes	Stop plateau 3.5 mmol/L
Reaching 45 mg/dL (nadir; 2.5 mmol/L)	J minutes	Start plateau nadir Stop constant insulin infusion
End of 45 mg/dL (nadir; 2.5 mmol/L)	J +30 minutes	Stop plateau nadir Start recovery
Reaching 72 mg/dL (4.0 mmol/L)	K minutes	Timepoint 4.0 mmol/L reached

* The PG level and duration of each plateau may vary due to patient's conditions as described in Safety Considerations for Assessment Plateaus in Appendix 6 of Protocol.

Counter-regulatory hormone responses, and responses of insulin and C-peptide to hypoglycemic clamp

Glucagon, growth hormone, cortisol, adrenaline, noradrenaline, insulin, and C-peptide concentrations at target PG levels of 100 mg/dL (5.5 mmol/L), 63 mg/dL (3.5 mmol/L), and 45 mg/dL (2.5 mmol/L) will be measured 3 times during each of these 3 plateaus (see [Table GPHG.4](#) for details).

- Mean concentrations at target PG levels of 100 mg/dL (5.5 mmol/L), 63 mg/dL (3.5 mmol/L), and 45 mg/dL (2.5 mmol/L) will be calculated from the 3 measurements taken during each of these 3 plateaus for PD analyses. If there is one missing measurement, the average value between 2 measurements will be used as the mean measurement. If there is only one value, it will be used as the measurement.

The concentrations are measured once at ambient PG (glucagon only) and upon recovery to 72 mg/dL (4.0 mmol/L) (see [Table GPHG.4](#) for details).

Table GPHG.4. Measurements of Glucagon, Insulin, C-peptide, Growth Hormone, Cortisol, Adrenaline, and Noradrenaline from Blood Sampling During Hypoglycemic Clamp Procedure on Day 79 and Day 80

Study Period Day	Clamp PG Level	Planned Timepoints* of Blood Sampling
Day 79		Only glucagon at ambient PG sample was measured in pre-prandial state prior to clamp initiation
Day 80	100 mg/dL (5.5 mmol/L)	-20 minutes -10 minutes 0 minutes
Day 80	63 mg/dL (3.5 mmol/L)	I + 10 minutes I + 20 minutes I + 30 minutes
Day 80	45 mg/dL (nadir; 2.5 mmol/L)	J + 10 minutes J + 20 minutes J + 30 minutes
Day 80	72 mg/dL (4.0 mmol/L)	K minutes

* The Planned Timepoints of blood sampling during clamp will be collected in eCRF.

Clinical hypoglycemia

Hypoglycemic symptom score

Symptoms of hypoglycemia will be measured with a subjective, validated questionnaire, the Edinburgh Hypoglycemia Symptom Scale (EHSS), which measures the intensity of commonly experienced hypoglycemic symptoms on a 7-point Likert scale (1 = No symptom, 2 = very mild, 3 = mild, 4 = mild to moderate, 5 = moderate, 6 = moderate to severe, and 7 = Severe). These symptoms have been grouped previously into neuroglycopenic symptoms (cognitive dysfunction and neuroglycopenia), and autonomic symptoms (McCrimmon et al. 2003).

In this study, 13 questions are used to measure hypoglycemic symptoms. These data will be recorded in eCRF.

- **Neuroglycopenic symptoms (10)**
 - **Cognitive dysfunction (6):** inability to concentrate, blurred vision, anxiety, confusion, difficulty speaking, and double vision
 - **Neuroglycopenia (4):** drowsiness, tiredness, hunger, and weakness
- **Autonomic symptoms (3):** sweating, trembling, and warmth

The subscores of neuroglycopenic symptoms (cognitive dysfunction and neuroglycopenia), and autonomic symptoms, and the overall score (means of non-missing values) will be calculated and used for PD analyses based on responses to 13 questions, where lower score indicates fewer symptoms.

The EHSS questionnaire will be administered twice (0 and 30 minutes) at each of the 3 plateaus (target levels of PG of 100 mg/dL [5.5 mmol/L], 63 mg/dL [3.5 mmol/L,] and PG of 45 mg/dL [2.5 mmol/L]) (see [Table GPHG.5](#) for details).

- The subscores and overall score (means of non-missing values) will be calculated for both collection timepoints in each plateau. Mean hypoglycemic symptoms subscores and overall score at each plateau (mean of the 2 measurements taken) will be calculated and used for analyses.

The EHSS questionnaire will be administered once when recovery PG of 72 mg/dL (4.0 mmol/L) is reached (see [Table GPHG.5](#) for details). The subscores and overall score for this single recovery collection timepoint will be used for analyses.

Table GPHG.5. Hypoglycemic Symptom Score and Hypoglycemia Awareness During Hypoglycemic Clamp Procedure on Day 80

Clamp PG Level	Planned Timepoints of Collecting Hypoglycemic Symptom Score and Hypoglycemia Awareness
100 mg/dL (5.5 mmol/L)	-30 minutes 0 minutes
63 mg/dL (3.5 mmol/L)	I minutes I + 30 minutes
45 mg/dL (nadir; 2.5 mmol/L)	J minutes J + 30 minutes
72 mg/dL (4.0 mmol/L)	K minutes

Hypoglycemia awareness

Hypoglycemia awareness will be evaluated based on the patients' response (yes/no) to the question "Do you feel hypoglycemic?" during induced hypoglycemia. These data will be recorded in eCRF.

Hypoglycemia awareness will be assessed twice (0 and 30 minutes) at each of the 3 plateaus (target levels of PG of 100 mg/dL [5.5 mmol/L], 63 mg/dL [3.5 mmol/L,] and PG of 45 mg/dL [2.5 mmol/L]) (see [Table GPHG.5](#) for details).

- If the patient answered "yes" at least once when the question was asked twice in the same plateau, the patient is aware of hypoglycemia during induced hypoglycemia at that target PG level. If the patient answered "no" to the question when asked twice in that plateau, the patient is unaware of hypoglycemia. If there is only one non-missing value, it will be used as the measurement.

Hypoglycemia awareness will be assessed once when recovery PG of 72 mg/dL (4.0 mmol/L) is reached (see [Table GPHG.5](#) for details).

Vital signs

Vital signs (that is, systolic blood pressure, diastolic blood pressure, pulse rate, and body temperature) at target PG of 100 mg/dL (5.5 mmol/L), 63 mg/dL (3.5 mmol/L), and 45 mg/dL (2.5 mmol/L) will be measured twice at each of the 3 plateaus (see [Table GPHG.6](#) for details).

- Mean vital signs (systolic blood pressure, diastolic blood pressure, and pulse rate) at target PG of 100 mg/dL (5.5 mmol/L), 63 mg/dL (3.5 mmol/L), and 45 mg/dL (2.5 mmol/L) will be calculated as the mean of the 2 measurements taken at each of these 3 plateaus for PD analyses. If there is only one non-missing value, it will be used as the measurement.

Vital signs will be measured once when recovery PG of 72 mg/dL (4.0 mmol/L) is reached (see [Table GPHG.6](#) for details).

Table GPHG.6. Vital Signs During Hypoglycemic Clamp Procedure on Day 80

Clamp PG Level	Planned Timepoints of Collecting Vital Signs
100 mg/dL (5.5 mmol/L)	-30 minutes 0 minutes
63 mg/dL (3.5 mmol/L)	I minutes I + 30 minutes
45 mg/dL (nadir; 2.5 mmol/L)	J minutes J + 30 minutes
72 mg/dL (4.0 mmol/L)	K minutes

6.9.2. Pharmacodynamic Statistical Inference

The counter-regulatory hormone responses (glucagon, growth hormone, cortisol, adrenaline, and noradrenaline), and responses of insulin and C-peptide will be reported in the International System of Units and conventional units.

6.9.2.1. Primary Pharmacodynamic Analysis

Glucagon counter-regulatory response during induced hypoglycemia

The primary PD parameter to assess the effect of tirzepatide 15 mg versus placebo will be the change in mean glucagon concentration from the target PG concentration of 100 mg/dL (5.5 mmol/L) to the nadir target 45 mg/dL (2.5 mmol/L) (i.e., glucagon at nadir PG – glucagon at PG of 100mg/dL) during induced hypoglycemia. This will be evaluated using a linear mixed-effect model, with treatment, treatment period, and treatment sequence as fixed effects, and patient as a random effect using restricted maximum likelihood (REML) method in PD analysis set.

Note: See Section [6.9.1](#) for calculation details. Mean concentrations of glucagon at target PG levels of 100 mg/dL (5.5 mmol/L) and 45 mg/dL (2.5 mmol/L) will be calculated from the 3

measurements taken during these plateaus, respectively. If there is one missing measurement, the average value between 2 measurements will be used as the mean measurement. If there is only value, it will be used as the measurement.

Inferential statistics will include least squares (LS) means and standard error of glucagon concentration change for tirzepatide versus placebo, the treatment difference (tirzepatide - placebo), 95% CI, and associated p-values.

Sensitivity analyses on primary endpoint among patients who reached nadir target PG of 45 mg/dL (2.5 mmol/L) will be conducted in a similar manner if deemed appropriate, otherwise summary statistics will be sufficient. Patients who reached nadir are defined as the ones whose mean PG is ≤ 45 mg/dL at J minutes (Start plateau nadir).

- The actual PG level at nadir (J minutes) will be summarized by treatment. The frequency and proportion of patients who did not reach target nadir will be summarized.

6.9.2.2. Secondary Pharmacodynamic Analysis

The following measurements will be secondary PD measures in the study. See Section [6.9.1](#) for data collection and calculation details.

Counter-regulatory hormone responses, and responses of insulin and C-peptide during induced hypoglycemia

Secondary PD measures to assess the effect of tirzepatide 15 mg versus placebo on counter-regulatory hormones, insulin, and C-peptide concentrations during induced hypoglycemia:

Glucagon

- Change in mean glucagon concentration from target PG concentration of 100 mg/dL (5.5 mmol/L)
 - to target PG concentration of 63 mg/dL (3.5 mmol/L)
 - to target recovery PG concentration 72 mg/dL (4.0 mmol/L)
- Change in mean glucagon concentration from ambient PG (see [Table GPHG.4](#) for details)
 - to target PG concentration of 100 mg/dL (5.5 mmol/L)
 - to target PG concentration of 63 mg/dL (3.5 mmol/L)
 - to target PG nadir 45 mg/dL (2.5 mmol/L)
 - to target recovery PG concentration of 72 mg/dL (4.0 mmol/L)

Insulin, C-peptide, growth hormone, cortisol, adrenaline, and noradrenaline

- Change in mean insulin, C-peptide, growth hormone, cortisol, adrenaline, and noradrenaline concentrations from target PG concentration of 100 mg/dL (5.5 mmol/L)

- to target PG concentration of 63 mg/dL (3.5 mmol/L)
- to target PG nadir 45 mg/dL (2.5 mmol/L)
- to target recovery PG concentration of 72 mg/dL (4.0 mmol/L)

The secondary PD parameters collected during hypoglycemic clamp procedure listed above (counter-regulatory responses) will be analyzed in a manner similar to the primary PD analysis using a linear mixed-effect model, respectively.

Additional assessments on counter-regulatory response are described in Section 6.9.2.3 as exploratory endpoints.

Time to hypoglycemia recovery

Secondary PD measures to assess the effect of tirzepatide 15 mg versus placebo on time to recovery from induced hypoglycemia:

- Time from termination of insulin infusion at PG concentration of nadir 45 mg/dL (2.5 mmol/L) to reach recovery PG concentration (72 mg/dL [4.0 mmol/L])
 - That is, $t_{PG_nadir-72}$ mg/dL [from Stop constant insulin infusion (J minutes) to the Timepoint 4.0 mmol/L reached (K minutes)]
 - The actual times (24 hour clock), corresponding to J and K minutes (see [Table GPHG.3](#) for details) will be identified by statistical programming, and the time interval will calculated for PD analyses.

The $t_{PG_nadir-72}$ mg/dL will be analyzed in a manner similar to the primary PD analysis using a linear mixed-effect model.

Clinical hypoglycemia

Secondary PD measures to assess the effect of tirzepatide 15 mg versus placebo on clinical hypoglycemia during induced hypoglycemia:

- Hypoglycemic symptoms score (subscores and overall score) at the following times:
 - at target PG concentration of 100 mg/dL (5.5 mmol/L)
 - at target PG concentration of 63 mg/dL (3.5 mmol/L)
 - at target PG concentration of nadir 45 mg/dL (2.5 mmol/L)
 - at target recovery PG concentration of 72 mg/dL (4.0 mmol/L)

The hypoglycemic symptom subscores and overall score at each of 4 target PG levels (i.e., 5.5 mmol/L, 3.5 mmol/L, nadir [2.5 mmol/L], and recovery [4.0 mmol/L]) during hypoglycemic clamp will be analyzed respectively in a manner similar to the primary PD analysis using a linear mixed-effect model.

- Hypoglycemia awareness (binary) at the following times:
 - at target PG concentration of 100 mg/dL (5.5 mmol/L)

- at target PG concentration of 63 mg/dL (3.5 mmol/L)
- at target PG concentration of nadir 45 mg/dL (2.5 mmol/L)
- at target recovery PG concentration of 72 mg/dL (4.0 mmol/L)

The hypoglycemia awareness at each of 4 target PG levels (i.e., 5.5 mmol/L, 3.5 mmol/L, nadir [2.5 mmol/L], and recovery [4.0 mmol/L]) during hypoglycemic clamp will be analyzed with nonparametric McNemar test at each target PG level to examine if there is difference in hypoglycemia awareness in comparison of tirzepatide 15 mg versus placebo.

The above PD parameters (hypoglycemic symptom scores and hypoglycemia awareness) collected at 4 target PG levels will be summarized by treatment using descriptive statistics. Corresponding plots on the hypoglycemic symptom scores with mean and standard deviations of PD parameters of these target PG levels will be provided by treatment.

Vital signs during induced hypoglycemia

Secondary PD measures to assess the effect of tirzepatide 15 mg versus placebo on vital signs during induced hypoglycemia:

- change in mean systolic blood pressure, diastolic blood pressure, and pulse rates from target PG concentration of 100 mg/dL (5.5 mmol/L)
 - to target PG concentration of 63 mg/dL (3.5 mmol/L)
 - to target PG nadir 45 mg/dL (2.5 mmol/L)
 - to target recovery PG concentration of 72 mg/dL (4.0 mmol/L)

The above changes in vital signs during induced hypoglycemia will be summarized by treatment, and will be analyzed respectively in a manner similar to the primary PD analysis using a linear mixed-effect model.

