$GIR [mL/hour] * concentration 20 \text{ g/100 mL} * 1000 \text{ mg/g} \div (60 \text{ min/hour}) \div \text{body weight [kg]}$

Exploratory PD measures to assess the effect of tirzepatide 15 mg versus placebo on glucose infusion related parameters include:

- Area under the glucose infusion rate curve from time of termination of insulin infusion until recovery (PG of 72 mg/dL [4.0 mmol/L]), $AUC_{GIR,PG_nadir-72 \text{ mg/dL}} [\text{mg/kg}]$
 - The time interval from Stop constant insulin infusion (J minutes) to Timepoint 4.0 mmol/L reached (K minutes) is of interest.
- The total amount of glucose infused to attain recovery (PG of 72 mg/dL [4.0 mmol/L]), $G_{\text{tot}} [\text{mg/kg}]$ (i.e. AUC of GIR)
 - The time interval from Start recovery (J+30 minutes) to Timepoint 4.0 mmol/L reached (K minutes) is of interest.
- The proportion of patients who require glucose infusion to attain recovery (PG concentration 72 mg/dL [4.0 mmol/L])
 - If the above calculated $G_{\text{tot}} > 0$, the patient required glucose infusion to attain recovery. If $G_{\text{tot}} = 0$, the patient attained recovery without glucose infusion.

- Average glucose infusion rate [mg/min/kg] from Start plateau 5.5 mmol/L (-30 minutes) to Stop constant insulin infusion (J minutes)
- Average glucose infusion rate [mg/min/kg] from Stop constant insulin infusion (J minutes) to Timepoint 4.0 mmol/L reached (K minutes)

Hypoglycemia recovery parameters

Exploratory PD measure to assess the effect of tirzepatide 15 mg versus placebo on the recovery from hypoglycemia include:

- PG achieved at the end of the spontaneous recovery period
 - This is the PG level at 45 minutes after termination of the insulin infusion (J minutes [Stop constant insulin infusion] + 45 minutes). At $J+45$ minutes, if PG doesn't recover to 72 mg/dL, Start constant glucose infusion.
- The proportion of patients who recovered spontaneously 45 minutes after termination of the insulin infusion ($J+45$ minutes)
- If the PG level at $J+45$ minutes ≥ 72 mg/dL, the patient recovered spontaneously at $J+45$ minutes.

The above other hypoglycemic clamp and recovery exploratory PD parameters (except the proportion of patients who require glucose infusion to attain recovery and the proportion of patients who recovered spontaneously at $J+45$ minutes) will be analyzed in a manner similar to the primary PD analysis using a linear mixed-effect model.

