The status of whether patients require glucose infusion to attain recovery and whether patients recovered spontaneously at $J+45$ minutes will be analyzed in a similar manner to the secondary analyses on hypoglycemia awareness with nonparametric McNemar test.

Counter-regulatory hormone responses, and responses of insulin and C-peptide, and vital signs during induced hypoglycemia

- Change in mean glucagon, insulin, C-peptide, growth hormone, cortisol, adrenaline, and noradrenaline concentrations from target PG nadir of 45 mg/dL (2.5 mmol/L) to 72 mg/dL (4.0 mmol/L)

The above changes in counter-regulatory responses will be analyzed in a manner similar to the primary PD analysis using a linear mixed-effect model.

- Change in vital signs (systolic blood pressure, diastolic blood pressure, and pulse rate) from target PG nadir of 45 mg/dL (2.5 mmol/L) to 72 mg/dL (4.0 mmol/L)

The above changes in vital signs during induced hypoglycemia will be analyzed in a manner similar to the primary PD analysis using a linear mixed-effect model.

Additional exploratory PD parameters (counter-regulatory responses, vital signs, and AUC_{GIR}) for analyses

The following PD parameters collected at ambient PG sample (only glucagon), three 30-min target PG plateaus (5.5 mmol/L, 3.5 mmol/L, and nadir [2.5 mmol/L]) and recovery [4.0 mmol/L] on Day 80 will be summarized by treatment using descriptive statistics. Corresponding plots of mean and standard deviations of these PD parameters over the target PG levels will be provided by treatment.

These PD parameters will be analyzed in a manner similar to the primary PD analysis using a linear mixed-effect model.

- Counter-regulatory hormone responses (glucagon, growth hormone, cortisol, adrenaline, and noradrenaline), and responses of insulin and C-peptide to induced hypoglycemia
 - Only glucagon will also be collected at ambient PG sample under pre-prandial state, prior to clamp initiation on Day 79
- Vital signs (systolic blood pressure, diastolic blood pressure, and pulse rate) during induced hypoglycemia
- AUC_{GIR} [mg/kg]
 - It will be calculated at each of the 3 plateaus (30 minutes each), and at recovery period ($J+30$ minutes to K minutes).

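### SAP 6.9.2.3's exploratory recovery rules can label a glucose-raised clamp as spontaneous recovery, code the same clamp as needing glucose, and read an infusion-raised PG as the spontaneous endpoint

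*SAP*

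**What the plan says.** **Time to recovery (secondary).** SAP 6.9.2.2 defines t as the interval "from Stop constant insulin infusion (J minutes) to the Timepoint 4.0 mmol/L reached (K minutes" and states that t in "mg/dL will be analyzed in a manner similar to the primary PD analysis using a linear mixed-effect model".

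**Recovery measures (exploratory).** SAP 6.9.2.3 adds these:
- *Recovered spontaneously*: if PG at J+45 is at or above "72 mg/dL, the patient recovered spontaneously at" that time. Nothing else is required.
- *Required glucose*: if G_tot is above zero, "the patient required glucose infusion to attain recovery". If G_tot is zero, recovery is taken as unaided. For G_tot, "The time interval from Start recovery (J+30 minutes) to Timepoint 4.0 mmol/L reached (K minutes) is of interest".
- *PG at the end of spontaneous recovery*: "This is the PG level at 45 minutes after termination of the insulin infusion".
- Each of the two yes/no items is compared by a McNemar test.

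**Clamp conduct (protocol Appendix 6).** The nadir plateau is held for up to 30 minutes after J, with variable glucose if needed. Constant glucose at 5.5 mg/kg/min starts at J+45 if PG is still below 72 mg/dL. It may start earlier for medical reasons, and variable glucose may be used to raise PG at any point in the clamp. PG falling below 40 mg/dL in recovery triggers a restart up to 45 mg/dL. After K, PG is actively raised to 100 mg/dL.

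**The concern.** The label *spontaneous* is tested only by a glucose value at one time, while the clamp allows that value to be produced by infusion. The companion item is tested by the amount infused over a different window. The two items look complementary but are not. One clamp can carry both codes, or be called unaided when it was not.

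The third measure has a related fault that needs no early rescue. A patient who reaches 72 mg/dL before J+45 then has PG driven upward by infusion, and the J+45 reading can include that rise.

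What is at stake is how far the exploratory recovery results can be trusted. Early glucose is given on symptoms and at the investigator's discretion. If it were more frequent on one treatment, that treatment would appear to have more spontaneous recovery, which is the wrong direction for a study meant to supply safety information.

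**Working it through.** The documents give no planned figure for recovery, so there is none to reproduce. The only planning number needed is the 30 completers: 30/0.80 = 37.5, rounded up to 38 enrolled, as SAP 5.2 states.

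**1. Do the rules conflict on permitted clamps?** I applied both rules minute by minute. From the documents: nadir 45 mg/dL, target 72 mg/dL, plateau to J+30, infusion 5.5 mg/kg/min. Assumed: glucose space V = 2.0 dL/kg and a constant unaided rise e from the end of the plateau. During infusion PG rises by e + 5.5/V = e + 2.75 mg/dL per minute. K is the first whole minute at or above 72.

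| Clamp | e (mg/dL/min) | Glucose to raise PG | K | PG ≥72 at J+45 | G_tot from J+30 (mg/kg) |
|---|---|---|---|---|---|
| A | 2.0 | none | J+44 | yes | 0 |
| B | 0.8 | from J+45 | J+50 | no (57) | 5 × 5.5 = 27.5 |
| C | 0.3 | from J+32 | J+41 | yes | 9 × 5.5 = 49.5 |
| D | 0.5 | from J+35 | J+43 | yes | 8 × 5.5 = 44.0 |
| E | 0.2 | from J+10 | J+20 | yes | window empty; 10 × 5.5 = 55 infused |

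Where K precedes J+45, the *yes* assumes that PG does not fall back below 72, since it is then raised toward 100.

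- A and B are coded consistently.
- C and D are coded both as recovered spontaneously and as requiring glucose. With glucose from J+32, this held at every combination tried (V = 1.6, 2.0 and 2.5 dL/kg; e = 0 to 1.5), with K between J+37 and J+45.
- E is coded spontaneous. If Start recovery is the actual time the plateau was stopped (J+10), G_tot is 55 and E carries both codes. With a nominal J+30 window, E would be coded as unaided.

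**2. How late can glucose start and still count as spontaneous?** With no unaided rise, 45 to 72 mg/dL takes 27V/5.5 minutes: 7.9, 9.8 and 12.3 for V = 1.6, 2.0 and 2.5. The latest start is 45 minus that: J+37.1, J+35.2 and J+32.7.

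**3. PG at J+45 after an earlier K.** Appendix 6's text starts the active rise after the recovery assessments; its clamp table starts variable glucose at K. The two should be reconciled. On either reading, glucose may run between K and J+45. The rate is variable; at an illustrative 5.5 mg/kg/min, ten minutes would add 55/V = 34, 28 and 22 mg/dL for V = 1.6, 2.0 and 2.5. The table also allows readings after K to be up to 30 minutes apart.

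**4. Size per clamp.** One misclassified clamp among 30 patients moves that treatment's proportion by 1/30 = 3.3 percentage points.

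**The case against.** The strongest reply is that these are exploratory measures, that the fault in the yes/no items arises only when glucose is given before J+45, and that the documents do not suggest this is common. If glucose starts only at J+45, the two rules agree. Some rescued clamps may also drop out, because the PD analysis set is limited to evaluable data from patients who complete both clamps. All of this stands and limits the size of the point. It does not remove it, because the rules give wrong labels on clamps that the protocol expressly permits.

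On PG at J+45, a K just before J+45 may still leave an unaided reading. That is fair: the value can reflect infused glucose, but need not.

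A reader might infer more than the documents support:
- **That t is wrongly analysed because aided and unaided recoveries are mixed.** The protocol defines t as insulin stop to 72 mg/dL and does not claim that recovery is unaided. The SAP already reports assistance alongside it: G_tot, the proportion requiring glucose, AUC of the infusion rate from J to K, "Average glucose infusion rate [mg/min/kg] from Stop constant insulin infusion (J minutes) to Timepoint 4.0 mmol/L reached (K minutes"), and an AUC_GIR for which "It will be calculated at each of the 3 plateaus (30 minutes each), and at recovery period". These do not repair the yes/no rules, but they answer the complaint about t.
- **That Start recovery is undefined.** SAP 6.9.1 takes key times from the actual eCRF clock times, and Table GPHG.3 ties Start recovery to the stop of the nadir plateau. The stated J+30 is the planned time.
- **That the treatment comparison is biased.** That would require early glucose to differ by treatment, and the documents give no rates.

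**Conclusion.** The point holds for three exploratory measures in SAP 6.9.2.3. The spontaneous-recovery rule lacks a no-glucose condition. It can contradict the required-glucose rule on the same clamp. The end-of-spontaneous-recovery PG can be an infusion-raised value whenever K precedes J+45.

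The contradiction follows from the definitions; the assumed glucose space and rise only illustrate it. The effect on the two proportions is 3.3 percentage points per misclassified clamp with 30 completers. The number of such clamps is unknown and may be zero. The third fault needs only a K before J+45, and how often that occurs is also not stated.

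The primary endpoint, the sample size, and the definition and model of t are not in error. This is a cheap improvement to the SAP.

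**What to change.** Change the SAP only; clamp conduct stays as it is.

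1. **One recovery variable.** Define spontaneous recovery as K at or before J+45, with G_tot = 0 from the actual eCRF Start recovery time to K, and no glucose given to raise PG between J and Start recovery. Glucose that only maintains the nadir plateau does not count. Code every other clamp as requiring glucose, including one with a below-40 restart in recovery, which G_tot already counts. No clamp then carries both codes, and one McNemar test serves.
2. **End-of-spontaneous-recovery PG.** Take the last PG at or before the earliest of K, the first PG-raising glucose after J, and J+45.
3. **Time to recovery.** Keep t and its mixed model. Beside the LS-mean difference, show by treatment the number of clamps assisted before J+45 and from J+45. This is description only: assistance arises after randomisation, so assisted and unassisted subsets do not compare like with like.

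**Cost.** SAP wording, some programming, and a blinded call on whether plateau glucose was raising or maintaining PG. PG readings, infusion rates and stage times are already recorded. Because t is untouched, this should not change a principal feature of the protocol (SAP 6.2) and can be logged in SAP Section 8. The downside is that glucose given for symptoms now counts as not spontaneous, so early-assisted clamps should also appear as a separate count.
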